1.2.2. Preclinical Pharmacology and Toxicology

Filgotinib and its metabolite, GS-829845 have been extensively characterized in nonclinical studies. This program includes cellular assays demonstrating potency and selectivity of the compound against JAK1; efficacy studies in rats and mice; repeat dose toxicity studies (up to 26 weeks in the rat and 39 weeks in the dog), in vitro and in vivo safety pharmacology and genetic toxicology studies, and reproductive toxicology studies in rats and rabbits. Additional toxicology studies conducted include phototoxicity studies and dose-range finding studies in support of a definitive rat juvenile toxicity study. A definitive juvenile toxicology study in rats is ongoing.

1.2.2.1. Nonclinical Pharmacology

In cellular assays, filgotinib inhibits JAK1 signaling with the concentration of an inhibitor that is required for 50% inhibition (IC_{50}) values of ≥ 179 nM, and demonstrates 30-fold selectivity over JAK2 in a human whole blood assay. Filgotinib has been profiled against 451 kinases and it is highly selective for JAK1; only 2.5% of kinases were inhibited $\geq 50\%$ at 50-fold higher concentration than IC_{50} for JAK1. Broad receptor profiling (~70 receptors, ion channels, transporters and enzymes) did not reveal any off-target liabilities of the compound. Filgotinib demonstrated high potency in the rat collagen-induced arthritis (CIA) model as well as in the mouse dextran sulfate sodium (DSS)-induced colitis model, the latter of which is detailed below. The major human metabolite of filgotinib, GS-829845, exhibits a similar JAK1 selectivity profile but is approximately 10-fold less potent as compared to parent filgotinib in vitro.

The efficacy of filgotinib was evaluated in a prophylactic setting of the chronic mouse DSS dextran model in 2 separate studies. Both studies evaluated oral dose levels of 10 and 30 mg/kg once daily. In addition to assessments of clinical score (disease activity index [DAI] and colon lesion score), serum markers of inflammation, immunohistochemical analysis, and expression of various chemokines and cytokines known to be altered in CD and UC patients were also evaluated in the distal colon of these mice.

In both studies, the DAI score, which takes into account body weight loss, rectal bleeding, and stool consistency, was reduced by filgotinib in a dose-dependent manner, demonstrating that filgotinib protected mice against colitis induced by DSS. Histology of the colon revealed a filgotinib-mediated dose-related reduction in colon lesion score, correlating with reductions in DAI score.

Additional endpoints evaluated across the DSS colitis model studies confirmed the suppression of various inflammatory markers including serum levels of C-reactive protein (CRP) and myeloperoxidase (MPO) and expression of IL 6 and TNF α (by reverse transcription polymerase chain reaction [RT-PCR]) by filgotinib. Immunohistochemical analysis of the colon confirmed inhibition of the JAK-STAT pathway by filgotinib as evidenced by a reduction of DSS-induced STAT3 phosphorylation.

1.2.2.2. Safety Pharmacology

Filgotinib and GS-829845 had no relevant effects on cardiovascular parameters (human-ether-a-go-go [hERG] and dog telemetry studies), apart from a slight non adverse increase in heart rate and arterial pressure with GS-829845 at exposures 8-fold that of the peak serum concentration (C_{max}) in subjects with CD treated with 200 mg once daily filgotinib. There were no relevant effects on electrocardiogram (ECG) and QT. Filgotinib and GS-829845 had no effects on the respiratory system and central nervous system (CNS).

1.2.2.3. Key Nonclinical Distribution, Metabolism, and Excretion Data

Filgotinib demonstrates good oral bioavailability in mice, rats, dogs, and mini-pigs but less in monkeys. Plasma protein binding is low (< 70%) in all species, including humans.

The pharmacokinetics (PK) of filgotinib is generally dose proportional without gender differences. No accumulation occurs with repeated dosing. The mean terminal half-life after oral administration is 4 hours and 5 hours in rats and dogs, respectively.

In the rat, filgotinib showed a rapid and even distribution throughout the body. High concentrations were observed only in the gastrointestinal (GI) tract and urinary bladder. Filgotinib does not penetrate into CNS tissues. The distribution of filgotinib indicates some affinity for melanin-containing tissues.

Excretion is nearly complete within 24 hours (rat) and 48 hours (dog) post-dosing. In the rat, fecal and urinary excretion accounted for 40% and 53% of the administered dose, respectively, with a bile secretion of about 15%. In the dog, fecal excretion was the primary route of excretion, accounting for 59% of the administered dose, with urinary excretion accounting for 25%.

In vitro metabolism studies in all species revealed one major metabolite (GS-829845). The formation of GS-829845 is mediated by carboxylesterases (CES) and is not dependent on cytochrome P450 (CYP).

In vitro experiments have shown that drug-drug interactions with filgotinib and GS-829845 are unlikely. There is no inhibition or induction of CYPs or uridine 5'-diphospho-glucuronosyltransferase (UGTs), and no relevant inhibition of key drug transporters, including organic anion transporters (OATs), by filgotinib or GS-829845. Organic cation transporter 2 (OCT2) was inhibited by both filgotinib (IC_{50} : 8.7 μ M) and GS-829845 (IC_{50} : 67 μ M). The clinical relevance of the IC_{50} values for inhibition of OCT2 will be further evaluated. MATE1 was also weakly inhibited by filgotinib (IC_{50} : 94 μ M) and GS-829845 (IC_{50} : > 100 μ M). Filgotinib was found to be a substrate of P-glycoprotein (P-gp).

1.2.2.4. Nonclinical Toxicology

In repeat oral dose toxicity studies in both rats and dogs, the primary target tissues identified for filgotinib were the lymphoid tissues which are expected based on the pharmacology of JAK inhibition. Additional filgotinib-related findings were observed in the male reproductive organs

of both species, and in the incisor teeth of rats only. Effects on the lymphoid system were fully reversible. Testicular toxicity demonstrated partial reversibility; however, sperm counts remained low. When using the mean exposure (AUC) at the NOAELs for the most sensitive species (the dog), the exposure margins compared to a 200 mg once daily dose of filgotinib in CD subjects are 2.5, 1.9, and 3.6-fold for the 26-week and 39-week chronic toxicity studies and the 39-week targeted exposure toxicity study, respectively.

GS-829845-related findings in the repeat-dose toxicity studies were generally similar to those of the parent filgotinib, however no testicular toxicity was noted following administration of GS-829845.

Filgotinib and GS-829845 were non-genotoxic when evaluated in the bacterial mutagenicity assay, the in vitro mouse lymphoma mutagenicity assay, and the rat bone marrow micronucleus assay.

In embryofetal development studies, filgotinib and GS-829845 caused embryo lethality and teratogenicity in pregnant rats and rabbits. Teratogenicity was observed at exposures slightly higher or similar to the human exposure at 200 mg once daily of filgotinib in subjects with CD. Administration of filgotinib did not affect female fertility but impaired fertility was observed in male rats at exposures approximately 12-fold the human exposure at 200 mg of filgotinib in subjects with CD. GS-829845 did not have any effects on fertility parameters in either male or female rats.

In an in vitro phototoxicity study in 3T3 cells, the metabolite GS-829845 was positive for phototoxic potential and results with filgotinib were equivocal. A follow-up in vivo rat phototoxicity assay revealed a lack of phototoxic potential for both compounds.

1.2.3. Clinical Trials of Filgotinib

An overview of exposure, safety, and efficacy in clinical studies conducted with filgotinib is available in the IB.

1.2.3.1. Phase 2 Study in Crohn's Disease (GLPG0634-CL-211, FITZROY)

A Phase 2, randomized, double-blind, placebo-controlled, multicenter study with filgotinib was performed in subjects with active CD with evidence of mucosal ulceration {Vermeire 2017}. In Part 1, a total of 174 subjects were randomized (3:1) to receive either filgotinib 200 mg once daily or placebo for 10 weeks. CCI

The efficacy of filgotinib was assessed by evaluating clinical remission (defined as CDAI score < 150), clinical response (defined as a decrease in CDAI of at least 100 points from baseline), and endoscopic response (defined as a decrease of at least 50% from baseline in the SES-CD score).

The primary endpoint of the study was met: at Week 10, 60 of 128 subjects (46.9%) who received filgotinib achieved clinical remission versus 10 of 44 subjects (22.7%) who received placebo, a difference of 24.1% (p-value = 0.0077). In addition, filgotinib treatment was associated with increases in the proportion of subjects with clinical response and endoscopic response compared with placebo.

Overall, the safety profile of filgotinib in CD subjects was consistent with prior studies.

1.3. Rationale for This Study

Accurate assessments of perianal disease activity may help to improve treatment and prognosis, and therefore the patient's quality of life. The Fistula Drainage Assessment (FDA) is one of the most widely used methods for the assessment, which takes the presence of purulent drainage from the cutaneous orifice after gentle compression as an index of activity. However, it does not take into account patient-reported outcomes. The Perianal Disease Activity Index (PDAI) is more comprehensive, as it evaluates perianal disease morbidity, particularly the presence of fistula discharge, pain and the restriction of daily activities, the restriction of sexual activity, the type of perianal disease, and the degree of induration. It is based on a simple 5-point scale, which can be easily used in an office setting, and is capable of quantifying the severity of perianal disease. A prospective study on 62 patients with perianal CD showed that the optimal PDAI cutoff value discriminating active and inactive perianal disease was > 4 , which had an accuracy of 87% detecting active disease when the clinical examination was considered the reference standard for comparison {[Losco 2009](#)}. In the same study, the PDAI cutoff was shown to be well-correlated with the clinical outcome as it indicated that a PDAI of ≤ 4 identified inactive disease requiring no therapy. This study will evaluate changes in PDAI score to assess the treatment response of perianal fistulizing CD to filgotinib.

Evaluation of the presence and severity of proctitis is critical in the management of patients with perianal fistulizing CD as it determines further treatment strategy and prognosis. The absence of proctitis is an independent predictor for increased healing and reduced recurrence rates of perianal fistulæ. However, rectal involvement is associated with a higher proctectomy rate compared with rectal sparing. In this study, centrally read flexible sigmoidoscopy will be conducted at baseline to assess the rectum and anal canal and the severity of proctitis determined by SES-CD will be used as one of the stratification factors. At Week 24, endoscopic appearance of the rectum and anal canal will be assessed again by centrally read flexible sigmoidoscopy.

Diagnostic modalities for fistulizing CD have improved over the last decade. An accurate assessment of each fistula's anatomy before treatment is essential, and enables the physician to choose the most appropriate therapy. Inadequate characterization of the fistula and associated pathology can result in potentially poor clinical outcomes. MRI is now considered the gold standard imaging tool to evaluate the perianal complication of CD as it offers excellent soft tissue discrimination with a wide field of view and it carries no radiation hazard {[Gecse 2004](#)}. Previous studies have shown that MRI is particularly sensitive for the detection of pelvic abscesses in CD patients, even in the absence of clinical signs {[Luniss 1994, Myhr 1994](#)}. Use of MRI as preinclusion clinical evaluation will ensure accurate characterization of the fistulæ and detect any abscess which may require drainage.

[figure not shown]
With the advent of anti-TNF therapy, the goal of treatment for fistulizing CD has evolved from symptomatic improvement (eg, by drainage) of the fistula to complete cessation of drainage and, in some patients, fistula closure and fibrosis of the fistula tract {[Gecse 2004](#)}. However, the optimal clinical index for assessing perianal CD is still under debate. Even though the endpoint adopted in previous trials in perianal fistulizing CD (ie, disappearance of drainage from at least 50% of the fistulae) {[Present 1999, Sands 2004](#)} is clinically relevant, it has been shown that cessation of drainage from external orifices does not accurately reflect what is happening to the fistula track. A small prospective cohort study including 18 subjects with perianal CD showed that persistent inflammatory activity in the fistula track is observed even after long-term (46 weeks) infliximab therapy, whereas external orifices are observed to heal and to stop draining rapidly after the therapy {[Van Assche 2003](#)}. A primary endpoint at 6 months into the treatment course was chosen to allow healing of the fistulae.

Residual inflammation of the fistula tract may be responsible for the occurrence of *de novo* perianal abscesses and for fistula recurrence in patients treated for fistulizing CD. The undetected pelvic abscess may become clinically apparent only after cessation of drainage from external orifices, and becomes a source of continuous inflammatory reaction. Given these challenges in assessing the activity and complications of the perianal CD, it may be warranted to combine MRI assessment with clinical examination to evaluate the efficacy of study treatment. A 2 cm cutoff for fluid collection as entry criteria was chosen as it represents the clinical threshold which warrants drainage. A cutoff of \leq 1 cm for fluid collection was chosen as part of the combined primary endpoint to ensure a more stringent definition of response to treatment was used that is differentiated from the clinical threshold for drainage.

In conclusion, this study will use MRI to evaluate healing of fistulae in addition to clinical assessment of drainage and fistula closure. MRI images will be centrally read in a blinded manner. These measures will provide a comprehensive and objective assessment of disease activity and treatment response in fistulizing CD.

1.4. Rationale for Dose

In Phase 2 trials in RA, pooled data with an exposure – response analysis demonstrated a dose-dependent increase in efficacy up to 200 mg total daily dose. In the Phase 2 study of CD (GLPG0634-CL-211), subjects treated in the 200 mg arm showed favorable response and remission rates (47% remission over 23% placebo and 59% response over 41% placebo). The remission rate at Week 20 for subjects who failed placebo for the first 10 weeks and commenced 100 mg from Weeks 10 to 20 was slightly lower (32%) though the response rate was comparable (59%), indicating some level of efficacy at the 100 mg dose. These results are consistent with the relationship observed between filgotinib exposures and inhibition of pSTAT1 activation (ex-vivo) following single and multiple filgotinib doses, where maximal inhibition of pSTAT1 activation (~78%) was achieved at or above 200 mg total daily dose and intermediate inhibition (~47%) at 100 mg {[Namour 2015](#)}. pSTAT1 data, in conjunction with considerations around the margin for nonclinical testicular findings, suggests assessing doses above 200 mg is not indicated. **CCI**

1.5. Risk/Benefit Assessment for the Study

Crohn's disease is a progressive and potentially life-threatening disease with few treatment options, many of which result in primary or secondary nonresponse. Inflammatory bowel disease may lead to increased risk of gastrointestinal malignancies, impairment in quality of life, and ultimate need for life-altering surgery. Current treatment options are limited in ability to establish mucosal healing and clinical remission and have significant safety and efficacy limitations; for example, biologics have significant immunogenic risks and steroids are associated with increased morbidity and mortality. Remission rates are generally low when compared to placebo rates across most therapies for IBD. There remains substantial unmet need in IBD, particularly in fistulizing CD among all phenotypes of CD. Despite the high cumulative occurrence and recurrence rates and significant morbidity associated with it, there is only 1 approved therapy for fistulizing CD.

Nonclinical studies in rats and dogs identified lymphoid tissues and testes as target organs for filgotinib in long-term repeat-dose toxicity studies. Although decreased lymphocyte numbers observed in nonclinical studies have not been seen in clinical studies, hematological assessment will be performed throughout the present study to ensure this potential risk is appropriately monitored. In both rats and dogs, microscopic findings in the testes included germ cell depletion and degeneration, with reduced sperm content and increased cell debris in the epididymis and reduction in fertility in male rats. The dog was determined to be the most sensitive species. When using the mean exposure (AUC) at the NOAELs for dogs in the 26- and 39-week chronic toxicity studies, and the 39-week targeted exposure toxicity study, the exposure margins compared with the highest proposed clinical dose of 200 mg once daily are 2.5-, 1.9-, and 3.6-fold respectively, in subjects with CD. A male safety study is planned to examine the potential effect of filgotinib on sperm/ejaculate parameters. Pending those results, the use of 200 mg in males in the United States with CD or UC will be limited to subjects who have failed at least two biologic therapies (TNF α antagonists or vedolizumab). Reference is made to the IB for further information about nonclinical testicular findings.

Administration of filgotinib produces an increase in embryofetal malformations in pregnant rats and rabbits at exposures similar to, or slightly higher than, exposures associated with a 200 mg once daily dose in CD subjects; this risk will be mitigated with the use of highly effective contraception for subjects of child-bearing potential.

JAK inhibition is expected to increase the risk of infection based on mechanism of action. Across global studies with filgotinib, in general, active treatment arms have increased incidences of infection versus placebo. In the present protocol, treatment interruption and discontinuation considerations surrounding infections are incorporated and sites and investigators will be trained regarding such circumstances. All subjects will be screened for tuberculosis (TB) and subjects with active infections will be excluded. Malignancy has been reported in subjects on filgotinib; in the present trial, subjects will be required to have up to date colorectal cancer screening and surveillance and subjects with recent malignancies will be excluded as outlined in the eligibility criteria. For further details about infections and malignancies, please reference the IB.

The potential benefits of JAK inhibition include improvement in clinical symptoms and mucosal and endoscopic healing. JAK inhibition may be efficacious in the treatment of IBD based on results from FITZROY. A lack of response contingency after Week 10 will enable early access to active drug when clinically indicated. In FITZROY, an increase in mean hemoglobin concentration was observed, without difference between filgotinib and placebo. No clinically significant changes from baseline in mean neutrophil counts or liver function tests were observed at 10 weeks. Filgotinib treated subjects showed an increase in HDL and no significant change in LDL. Lipid and hemoglobin effects represent potential benefits in this population.

An independent data monitoring committee (DMC) appointed to monitor the study will provide an additional level of risk mitigation. The DMC may advise to continue the study unchanged, to modify the study, or to discontinue the study. The initial meeting will occur after approximately 20% of the planned total number of subjects reach the Week 10 visit. Following this, the next meeting will occur after approximately 50% of subjects reach the Week 10 visit. Additional DMC meetings may be convened, if needed.

Taking all of these considerations into account with respect to the filgotinib program, the early signals for efficacy demonstrated in the CD clinical trials, as well as the beneficial findings in nonclinical models of disease and the overall safety, tolerability, and PK characteristics of filgotinib that have been elucidated to date, there is a favorable benefit-risk profile for this agent in continued development as a treatment for fistulizing CD. The overall risk/benefit balance of this study is considered favorable.

For additional information about the risks of filgotinib, reference is made to the filgotinib IB.

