* Non-responders (luminal disease) are defined as subjects who either had a baseline CDAI score ≥ 220 and never achieve a ≥ 70 -point CDAI reduction from baseline at any point up to and including Week 10 OR had a baseline CDAI score < 220 and have an increase in CDAI of ≥ 100 points from baseline, with CDAI ≥ 220 at Week 10. Non-responders (perianal fistulizing disease) are defined as subjects who meet the following criteria for PDAI symptom subscores : "Discharge" subscore of >1 and ≥ 1 -point increase from baseline at Week 6 and Week 10 OR "Pain/restriction of activities" subscore of >1 and ≥ 1 -point increase from baseline at Week 6 and Week 10

** Disease worsening is defined as an increase in CDAI of ≥ 100 points from the Week 10 value with CDAI score ≥ 220 points at 2 consecutive visits

*** Subjects who are non-responders, meeting disease worsening criteria, or complete the study at Week 24, will have the option to enter a separate LTE study, if eligible.

Treatment group 1 (n=30): filgotinib 200 mg and placebo-to-match (PTM) filgotinib 100 mg, once daily

Treatment group 2 (n=30): filgotinib 100 mg and PTM filgotinib 200 mg, once daily

Treatment group 3 (n=15): PTM filgotinib 200 mg and PTM filgotinib 100 mg, once daily

Note: United States (US) males who have not failed at least 2 prior biologic therapies (any tumor necrosis factor-alpha [TNF α] antagonist and vedolizumab) will be randomized in a 2:1 ratio to either filgotinib 100 mg or matching placebo.

For the purposes of this protocol, US males who have failed at least one prior TNF antagonist and present with actively draining perianal fistulae despite concomitantly taking vedolizumab at Day 1 will be considered as dual refractory patients. This assessment is based on recently published data from a subgroup analysis of the GEMINI-2 study, showing a beneficial effect of vedolizumab treatment for patients that were randomized with actively draining perianal fistulae at baseline {Feagan 2018}.

Treatment assignments will be stratified by:

- Anatomy of draining perianal fistulae at screening determined by MRI (simple *versus* complex)
- Receiving vedolizumab therapy concomitantly at Day 1 (Yes or No)
- Presence of moderately to severely active proctitis (Yes or No)

This study includes:

- Screening (Day -30 to -1)
- Randomization (Day 1)
- Blinded treatment (Day 1 to Week 24)

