3.3. Study Treatments

Based on protocol eligibility criteria, subjects will be screened for enrollment and randomized into 1 of 3 treatment groups in a blinded fashion in a 2:2:1 ratio as follows:

Treatment group 1 (n = 30): filgotinib 200 mg and PTM filgotinib 100 mg, once daily

Treatment group 2 (n = 30): filgotinib 100 mg and PTM filgotinib 200 mg, once daily

Treatment group 3 (n = 15): PTM filgotinib 200 mg and PTM filgotinib 100 mg, once daily

Note: US males who are not dual refractory will be randomized in a 2:1 ratio to either filgotinib 100 mg or matching placebo. For the purposes of this protocol, US males who have failed at least one prior TNF antagonist AND either previously failed vedolizumab induction therapy or are concomitantly taking vedolizumab at Day 1 and present with actively draining perianal fistulae despite continued vedolizumab therapy will be considered as dual refractory patients. This assessment is based on recently published data from a subgroup analysis of the GEMINI-2 study, showing a beneficial effect of vedolizumab treatment for patients that were randomized with actively draining perianal fistulae at baseline (Feagan 2018).

Treatment assignments will be stratified according to the following factors:

- Anatomy of draining perianal fistulae at screening determined by MRI (simple *versus* complex)
- Receiving vedolizumab therapy concomitantly at Day 1 (Yes or No)
- Presence of moderately to severely active proctitis (Yes or No)

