8.8. Sample Size

A total of approximately 75 subjects are planned to be randomized (2:2:1 ratio); 30 subjects to each of the filgotinib dose groups and 15 subjects to the placebo group. This sample size is considered adequate to assess the safety, tolerability, and efficacy of filgotinib in a descriptive manner.

Table 8-1 provides the exact 90% CI using the binomial distribution for a given combined fistula response rate ranging from 20% to 80%:

Table 8-1. Combined Fistula Response Rates (90% CI)

Number Randomized	Number of Responders	Response rate	Lower Limit of 90% CI	Upper Limit of 90% CI
30	6	20%	9%	36%
30	9	30%	17%	47%
30	12	40%	25%	57%
30	15	50%	34%	66%
30	18	60%	43%	75%
30	21	70%	53%	83%
30	24	80%	64%	91%

CI = confidence interval

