8.9. Data Monitoring Committee

An external data monitoring committee (DMC) comprised of an independent statistician and two independent gastroenterologists will review the progress of the study and perform interim reviews of safety data and provide recommendation to Gilead whether the nature, frequency, and severity of adverse effects associated with study treatment warrant the early termination of the study in the best interests of the participants, whether the study should continue as planned, or the study should continue with modifications.

The DMC will meet twice to evaluate all available safety data of the study. The initial meeting will occur after approximately 20% of the planned total number of subjects complete their Week 10 visit. Following this, the next meeting will occur after approximately 50% of the subjects reach Week 10. Additionally, the DMC members may request an unscheduled review of the study data based on a concern for subject safety. An ad hoc DMC meeting may be triggered by the following conditions:

- ≥ 2 subjects develop the same (by PT) related, Grade 4, unexpected AE in the infections and infestations SOC
- ≥ 2 subjects develop any related, Grade 4, thromboembolic events that have been positively adjudicated by the adjudication committee (see Section 8.10)
- Any subject develops a Grade 5, related, unexpected AE. The definition of an unexpected AE will be based on the reference safety information that is on file at the time the event occurs

After a minimum of 35 subjects (estimated to be 7 from placebo group and 14 from each filgotinib treatment group based on randomization ratio) are enrolled and complete Week 10 visit or discontinue from the study, an interim futility analysis will be conducted to evaluate efficacy improvement in fistulizing disease. The cumulative safety analysis and summary statistics to evaluate perianal fistula closure of external openings, and CCI [REDACTED]

[REDACTED] improvement will be generated and provided to the DMC. The DMC will make a recommendation to either continue the study without modification or recommend that the study be halted due to lack of efficacy, and will be based on the totality of data available at the time of the interim analysis.

The DMC's specific activities will be defined by a mutually agreed upon charter, which will define the DMC's membership, conduct and meeting schedule.

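### The rule restricting 200 mg in US males is worded differently in the synopsis, Section 1.5 and Section 3.3, and two patient profiles are treated differently as a result

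*Protocol*

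**What the plan says.** Four places in the protocol and one in the SAP bear on which US males may receive 200 mg.

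- **Protocol 1.5 (Risk/Benefit).** While a male safety study is pending, 200 mg in US males with CD or UC "will be limited to subjects who have failed at least two biologic therapies". The parenthesis that follows names TNF antagonists or vedolizumab.
- **Protocol synopsis, stream sentence.** This concerns US males without failure of at least two earlier biologics. Its parenthesis opens with any TNF-alpha and runs on: "antagonist and vedolizumab) will be randomized in a 2:1 ratio to either filgotinib 100 mg or matching placebo".
- **Protocol synopsis, label sentence.** US males with at least one TNF failure who "present with actively draining perianal fistulae despite concomitantly taking vedolizumab at Day 1 will be considered as dual refractory patients". Earlier vedolizumab failure is not mentioned here.
- **Protocol 3.3 (Study Treatments).** "US males who are not dual refractory will be randomized in a 2:1 ratio to either filgotinib 100 mg or matching placebo". To be dual refractory, a man needs a TNF failure and must have "either previously failed vedolizumab induction therapy or are concomitantly taking vedolizumab at Day 1", in the latter case with fistulae still draining.
- **SAP 1.2.** Repeats the Section 3.3 definition.
- **Protocol 5.3.** Uses dual refractory, without defining it, to decide which open-label dose a US male is offered after disease worsening.

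The eligibility criteria do not contain the rule. Sections 4.1 and 6.1 give 2:2:1 for everyone and do not mention the US-male exception. No passage says which wording governs.

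**The concern.** The restriction decides which randomisation stream a US male enters: 2:2:1 with 200 mg available, or 2:1 without it. It is also the protocol's stated response to the nonclinical testicular findings. Section 1.5 counts any two failures from a pooled list. Section 3.3 requires one failure from each of two classes and, for past vedolizumab use, names induction failure only. The synopsis does not restrict vedolizumab failure to induction in its stream sentence, but its label drops past failure altogether.

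A site or a system builder working from one section could therefore classify a man differently from someone working from another. At stake are that man's allocation probabilities, the match between the safeguard as justified and the safeguard as applied, and the open-label dose offered later under Section 5.3.

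**Working it through.** **Plan's own figures.** Protocol 8.8 states: "A total of approximately 75 subjects are planned to be randomized (2:2:1 ratio); 30 subjects to each of the filgotinib dose groups", with 15 on placebo. At 2:2:1, 75 × 2/5 = 30, 75 × 2/5 = 30 and 75 × 1/5 = 15. Section 8.9 gives the interim sizes as "estimated to be 7 from placebo group and 14 from each filgotinib treatment group based on randomization ratio"; 35 × 2/5 = 14 and 35 × 1/5 = 7. Both reproduce.

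**Each wording applied to the same men.** All are US males.

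| Profile | 1.5 limit | Synopsis, stream sentence | Synopsis, label | 3.3 and SAP 1.2 |
|---|---|---|---|---|
| (i) Two TNF failures, never on vedolizumab | Inside | 2:1 if both classes are required; 2:2:1 if the parenthesis is only a list of agents that count | Outside | 2:1 |
| (ii) One TNF failure; lost response to vedolizumab after induction, now stopped | Inside | 2:2:1 | Outside | 2:1, read literally |
| (iii) One TNF failure; failed vedolizumab induction, off it at Day 1 | Inside | 2:2:1 | Outside | 2:2:1 |
| (iv) One TNF failure; draining fistulae on vedolizumab at Day 1 | Inside only if ongoing vedolizumab counts as failed | 2:2:1, through the label sentence | Inside | 2:2:1 |

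Profile (i) separates Section 1.5 from Section 3.3 on either reading of the synopsis. Profile (ii) separates the synopsis from Section 3.3. Profiles (iii) and (iv) keep the same stream in the synopsis and in Section 3.3.

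Profile (iii) matters for Section 5.3 instead. After disease worsening, that section offers US males 100 mg open label unless they are dual refractory. He is dual refractory by Section 3.3 but not by the synopsis label.

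**Size for one man whose stream depends on the wording.**

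- 200 mg: 2/5 = 40% or 0%
- 100 mg: 2/5 = 40% or 2/3 = 66.7%
- Placebo: 1/5 = 20% or 1/3 = 33.3%

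**Size for the trial.** The number of such men, k, is not in the documents, so it is an assumption. Moving one man from 2:2:1 to 2:1 changes the expected arm sizes by 0 − 2/5 = −0.40 (200 mg), 2/3 − 2/5 = +0.27 (100 mg) and 1/3 − 1/5 = +0.13 (placebo).

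| k (assumed) | 200 mg | 100 mg | Placebo |
|---|---|---|---|
| 0 | 0 | 0 | 0 |
| 1 | −0.4 | +0.27 | +0.13 |
| 5 | −2.0 | +1.33 | +0.67 |
| 10 | −4.0 | +2.67 | +1.33 |

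**The case against.** The strongest reply is that the operational text is consistent. Section 3.3 is the study-treatment section, and SAP 1.2 repeats it. Section 1.5 is a programme-level statement: it speaks of CD or UC although this trial excludes UC, and it names no ratio or stream. It also sets a limit rather than an entitlement. If Section 3.3 keeps some men inside that limit away from 200 mg, it is stricter and the limit is not exceeded. This stands. A reader might infer that two TNF failures entitle a man to 200 mg under Section 1.5, or that the safeguard has been breached; the text supports neither.

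A reader might also infer that profiles (iii) and (iv) change stream. They do not. Under the synopsis, allocation turns on the stream sentence, which keeps profile (iii) in 2:2:1. Profile (iv) is expressly treated as dual refractory in the synopsis, Section 3.3 and SAP 1.2.

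Two further arguments add nothing to the size of the problem. The exposure margins of 1.9- to 3.6-fold describe 200 mg in CD subjects under any wording. Unequal access to 200 mg between the two streams, and its effect on comparability with placebo, comes from having a 2:1 stream at all; aligning the words would not remove it.

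What the reply does not dispose of is profile (ii), where the synopsis and Section 3.3 conflict on the stream itself, and the undefined term in Section 5.3. Nor does any clause settle the matter. The instruction in Section 7.6 to apply the more conservative criteria belongs to toxicity management, not to allocation.

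**Conclusion.** The point holds as an internal inconsistency: the text is wrong as written, with moderate severity. The wordings differ in current text. Two profiles, (i) and (ii), are treated differently, with a chance of 200 mg of 40% or 0% depending on the wording applied. For profile (iii) the stream does not change, but the label that governs the open-label offer does.

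This rests on reading Section 3.3 literally, so that vedolizumab failure after induction is not induction failure. For profile (i), the 40% also assumes that the count in Section 1.5, or the list reading of the synopsis, is used to assign the stream.

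A reader might conclude that men were sent to the wrong stream. The documents cannot show this: treatment comes from the IWRS, whose specification is not among them, and the number of men affected is not given.

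**What to change.** Reconcile the synopsis, Protocol 1.5, 3.3 and 5.3, and SAP 1.2 to a single definition, stated once and referred to elsewhere. It should settle three things explicitly: whether two failures within the TNF class count, whether vedolizumab failure after induction counts, and whether past vedolizumab failure falls under dual refractory for the purpose of Section 5.3. Sections 4.1 and 6.1 should refer to the exception. Then confirm that the IWRS question uses the same words. No position is taken here on which definition is right.

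The cost is protocol and SAP wording plus a specification check. Aligning the words changes no analysis method; whether it changes the allocation of future subjects depends on what the IWRS already uses.
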